**Table 6-4. MT-3724 Dose Modification Guidance and Specific Management of Toxicities**

	Specific Management	MT-3724 Dose Modificationa
Nonhematological TEAEs		
Grade $\geq$ 2 CRS	
Subjects should be closely monitored for signs of CRS. This includes:
 

Monitoring of vital signs (temperature, heart rate, BP, respiration rate), body weight and clinical symptoms including headache, myalgia, muscle weakness, edema, neurological and gastro-intestinal symptoms, abdominal pain, and fatigue

Monitoring of laboratory parameters of hematology, albumin, kidney and liver function and cytokines in case of clinical symptoms indicative of CRS

 
Investigators should consider supportive measures while on trial regardless of dosing or timing of dosing.
	May trigger a modification of MT-3724 treatment (dose interruption, dose delay, dose reduction or permanent discontinuation) if deemed at least possibly related to MT-3724 by the investigator.

**Table 6-4. MT-3724 Dose Modification Guidance and Specific Management of Toxicities**

	Specific Management	MT-3724 Dose Modificationa

Grade <math>\geq</math> 2 CLS: As defined in CTCAE v5.0, or if at least 2 of the following within the same cycle (unless unequivocally related to underlying condition) reaches the level of Grade 2:
 
 
• Hypoalbuminemia
 
• Hypotension
 
• Edema (peripheral or central, all types) and/or weight gain
 
	
Subjects should be closely monitored for signs of CLS. This includes:
 
 
• Monitoring of vital signs (temperature, heart rate, BP, respiration rate), body weight, edema of any type including both peripheral edema and central edema (such as pleural effusion or signs of dyspnea).
 
• Monitoring of laboratory parameters including hemoconcentration (eg, hematocrit, Hb), and especially albumin and CK in case of clinical symptoms indicative of CLS.
 
 
Investigators should consider supportive measures while on trial regardless of dosing or timing of dosing. If a subject experiences Grade 2 hypotension, orthostasis, edema, or hypoalbuminemia, normal saline and/or an albumin infusion may be given, as needed.
	
Treatment modification due to CLS:
 
 
• For Grade <math>\geq</math> 3 CLS, the MT-3724 treatment must be permanently discontinued.
 
• For Grade 2 CLS, the MT-3724 treatment must be held, and may only be restarted after: 
 
◦ a minimum of 7 days has elapsed after onset of CLS, and
 
◦ all signs and symptoms of CLS have resolved to at least grade 1, and
 
◦ albumin has remained <math>\geq</math> 3.0 g/dL for at least 5 days post last albumin infusion (if required) without additional albumin substitution
 
 
 
 
Subsequent doses of MT-3724 must be:
 
 
• reduced by at least 25%, and
 
• administered once weekly
 
 
or subject may be permanently discontinued at the investigator's discretion.

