### **Cohort 1:**

The starting MT-3724 dose for each subject will be 10 µg/kg for the first 2 doses (D1, D3) and then increased to 25 µg/kg for the remaining doses (D5, D8, D10, D12) of the first 21-day cycle and all doses of Cycle 2 (D1, D3, D5, D8, D10, D12). Dosing will then continue at 25 µg/kg weekly (D1, D8, D15), beginning with Cycle 3 ([Table 6-1](#)).

If fewer than 2/6 subjects have a DLT in Cohort 1, then the study will proceed to Cohort 2. If 2 or more subjects have a DLT in Cohort 1, the study will be stopped.

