### **Cohort 2:**

The starting MT-3724 dose in each subject will be 10 µg/kg for the first 2 doses (D1, D3). The dose will then be increased to 25 µg/kg for 2 doses (D5, D8) and then the dose will be increased to 50 µg/kg for the remaining doses (D10, D12) of the first 21-day cycle and all doses of Cycle 2. Dosing will then continue at 50 µg/kg weekly (D1, D8, D15) beginning with Cycle 3 ([Table 6-1](#)).

If fewer than 2/6 subjects have a DLT in Cohort 2, then the study will continue to Part 4 using the Cohort 2 dose and schedule. If 2 / 6 subjects experience a DLT in Cohort 2, the study will continue to Part 4 using the Cohort 1 dose and schedule.

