### 6.2.1 Dose Modification for Treatment-emergent Adverse Experiences

The following actions are recommended after any of the TEAEs listed in [Table 6-4](#) occur.

- The investigator should notify the medical monitor acting on behalf of the sponsor about the TEAE within 24 hours of the awareness.
- The investigator should monitor the subject and if necessary, perform unscheduled diagnostic procedures and therapeutic interventions, including those not specified in the study protocol.
- If a subject experienced Grade  $\geq 2$  IRR, or another Grade  $\geq 2$  hypersensitivity event, Grade  $\geq 2$  CRS or Grade  $\geq 2$  CLS, then the investigator should obtain serum samples for

cytokines, complement, and histamine as soon as possible after the TEAE onset. These samples should be marked “STAT” and shipped immediately to the central laboratory.

- MT-3724 dose may be reduced at the investigator’s discretion. See [Table 6-3](#) for recommended dose reduction steps. The number of MT-3724 dose reductions per subject is not limited, except that the reduced dose cannot be < 5 µg/kg/dose (this is the lowest dose tested in the clinic so far).
- No intra-subject escalation of MT-3724 dose is permitted after previous MT-3724 dose reduction.
- MT-3724 treatment may be **restarted** if the TEAE that previously led to treatment modification has resolved to Grade ≤1 or the subject’s baseline within the time frame deemed appropriate at the investigator’s discretion.
  - After the resolution of the TEAE, the MT-3724 dose for continued treatment may be the same or reduced, as determined according to the stopping rules (if applicable) or at the investigator’s discretion

MT-3724 treatment must be **permanently discontinued** if a TEAE that previously led to treatment modification did not resolve to Grade ≤1 or baseline within 14 days.

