**Table 6-3. Dose Reduction Steps**

Dose Reduction a	Dose µg/kg/dose		
	10	25	50
Full Dose			
First Reduction (~ 25%)	8	19	38
Second Reduction (~ 50%)	5	13	25

a Other reductions require consultation and agreement of the medical monitor.

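### The first reduction steps in Table 6-3 (8, 19 and 38 µg/kg) fall just short of the 25% minimum cut that Table 6-4 requires after Grade 2 capillary leak syndrome

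*Protocol*

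**What the plan says.** The Grade 2 CLS entry in Table 6-4 holds treatment for at least 7 days and sets conditions for restart. It then says: "Subsequent doses of MT-3724 must be" "reduced by at least 25%, and" given once weekly. The alternative is permanent discontinuation. The entry does not say which dose the cut is taken from.

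Section 6.2 lists dose reduction as one of the permitted modifications and refers to Table 6-3 for it. That table has columns for full doses of 10, 25 and 50 µg/kg. The row whose label begins "First Reduction (~ 25" (that is, about 25%) gives 8, 19 and 38. The second row, labelled as about 50%, gives 5, 13 and 25. The table's footnote adds: "Other reductions require consultation and agreement of the medical monitor".

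Footnote a of Table 6-4 puts one dose level at roughly 25% to 33%, citing Table 6-3, and asks for discussion of actual amounts with the sponsor and medical monitor. Section 6.2.1 calls the Table 6-3 steps recommended. It says that once an event has resolved, "the MT-3724 dose for continued treatment may be the same or reduced", and that "No intra-subject escalation of MT-3724 dose is permitted after previous MT-3724 dose reduction".

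**The concern.** The CLS rule is a floor, and the protocol's own reduction table appears not to reach it. A site that reads Table 6-4, turns to Table 6-3 as Section 6.2 directs, and takes the first step labelled as about 25% would under-reduce without noticing.

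The rule matters because Version 11 was written after a Grade 5 CLS event. Its rationale (Section 12.1) links CLS to dose, and to the days after initial dosing or after re-dosing following a first CLS. Restart after CLS is thus a risk point that the sponsor itself identified. Section 2.2.1 reports two of the five earlier CLS cases at 10 µg/kg and one at 25 µg/kg. Those three came from the combination studies. In this monotherapy study, CLS is reported only at 75 and 50 µg/kg. At stake is the safe restart of a few subjects, not the efficacy conclusion.

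**Working it through.** **Inputs.** Full doses 10, 25 and 50 µg/kg, first steps 8, 19 and 38, and second steps 5, 13 and 25 (Table 6-3). Required cut of at least 25% (Table 6-4, CLS row). One dose level of about 25% to 33% (Table 6-4, footnote a).

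**Reproducing the table.** Take 0.75 and 0.50 of each full dose and round half up to a whole µg/kg:
- 0.75: 7.5 → 8; 18.75 → 19; 37.5 → 38.
- 0.50: 5 → 5; 12.5 → 13; 25 → 25.

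All six printed entries are recovered, so the first steps are 25% cuts rounded upward.

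**Actual cuts, and distance from the ceiling.** Cut = 1 − reduced/full. The highest dose that meets the rule is 0.75 × full.

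| Full dose | Ceiling (75%) | First step | Cut | Excess over ceiling |
|---|---|---|---|---|
| 10 | 7.5 | 8 | 1 − 8/10 = 20% | 0.5 (0.5/7.5 = 6.7%) |
| 25 | 18.75 | 19 | 1 − 19/25 = 24% | 0.25 (0.25/18.75 = 1.3%) |
| 50 | 37.5 | 38 | 1 − 38/50 = 24% | 0.5 (0.5/37.5 = 1.3%) |

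All three cuts are below 25%, and so below the range in footnote a.

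**Second steps.** 1 − 5/10 = 50%; 1 − 13/25 = 48%; 1 − 25/50 = 50%. These comply, but cut about twice as much as the rule asks.

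**Per infusion.** The infusion caps correspond to 120 kg (1200/10 = 3000/25 = 6000/50 = 120). At that weight the excess is 0.5 × 120 = 60 µg, 0.25 × 120 = 30 µg and 0.5 × 120 = 60 µg.

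**Rounding down instead.** 7, 18 and 37 µg/kg are cuts of 1 − 7/10 = 30%, 1 − 18/25 = 28% and 1 − 37/50 = 26%. All meet the rule, lie within 25% to 33%, and stay above the 5 µg/kg minimum in Section 6.2.1.

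**The case against.** The best defence is that a site can comply with the text as it stands. Table 6-3 marks its steps as approximate, and Section 6.2.1 calls them recommended. The CLS row does not ask for a cut of one dose level, as the neutropenia and hepatotoxicity rows do. It sets its own floor, and the more specific instruction governs. Footnote a already calls for consultation on the actual amount. The excess is also smaller than a drift that the protocol accepts elsewhere, since Section 6.1.1.2 generally requires recalculation only when weight changes by 10% or more.

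This settles the size of the problem but not its existence. An approximate label explains the table, yet a 20% cut does not satisfy a minimum of 25%. Section 6.2 names Table 6-3 as the basis for reductions, and footnote a equates one step of that table with at least about 25%. The smallest compliant cut appears nowhere in the table.

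A reader might go further. Because the CLS row names no reference dose, the cut could seem to apply to the next planned dose. In Cohort 1 the planned dose rises to 25 µg/kg "for the remaining doses (D5, D8, D10, D12) of the first 21-day cycle". After CLS at 10 µg/kg on Day 3, that would permit 0.75 × 25 = 18.75 µg/kg (19 in the table), about 1.9 times the dose at which CLS occurred. The documents do not support this:
- Section 6.2.1 limits the restart dose to the same or a lower one.
- Section 10.3.7 says that a dose increase is not an available action in adverse-event management.
- The Table 1-2 note, under which a delayed dose keeps its number, concerns the timing of PK samples and does not assign doses.
- The hold of at least 7 days and the move to weekly dosing take the subject off the step-up sequence.

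What remains is missing detail. The row is silent on the reference dose, Section 6.2.1 introduces its actions as recommended, and its escalation bar applies only once a reduction has been made.

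**Conclusion.** The first reduction steps are wrong as written for use after Grade 2 CLS: 20%, 24% and 24% against a mandatory minimum of 25%. Severity is minor. The shortfall is 5 percentage points at 10 µg/kg and 1 point at 25 and 50 µg/kg.

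The unstated reference dose deserves a clarifying sentence, not a finding of its own. The last dose given is the natural reading of Sections 6.2.1 and 10.3.7.

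The conclusion rests on the protocol text alone. The CLS management guide named in Section 2.2.2 is not among the documents and may give its own restart doses. The documents give no rate of Grade 2 CLS under step-up dosing, so the number of affected subjects cannot be estimated. Nothing here alters the Part 4 sample size, decision rule or response-rate analysis.

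**What to change.** **Table 6-3.** Round the first steps down to 7, 18 and 37 µg/kg, or cap them at 7.5, 18.75 and 37.5 if the pharmacy can prepare those doses. Because Table 6-3 serves every toxicity, whole-number rounding lowers the first step for all reductions: by 1/8 = 12.5%, 1/19 = 5.3% and 1/38 = 2.6% of the present entries. If that is unwanted, a footnote can confine the lower values to restart after CLS.

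**Table 6-4, CLS row only.** State that the cut is taken from the last dose given before CLS onset and that the subject does not resume the scheduled step-up. This confirms what Sections 6.2.1 and 10.3.7 already imply. It should not go into Section 6.2.1 as a general rule, because there it would also hold back subjects reduced at lead-in for other toxicities. The CLS management guide should use the same wording.

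**Cost.** Three table entries and one or two sentences, with no extra subjects, procedures or analyses. A few subjects with CLS at lead-in would stay at a low dose: 7.5 µg/kg is 7.5/25 = 30% of the Cohort 1 target and 7.5/50 = 15% of the Cohort 2 target.

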**Table 6-4. MT-3724 Dose Modification Guidance and Specific Management of Toxicities**

		Specific Management	MT-3724 Dose Modification a
SCr increase $\geq$ 1.5-3.0 times above baseline or 1.5-3.0 x ULN in the absence of dehydration or bleeding			May trigger a modification of MT-3724 treatment (dose interruption, dose delay, dose reduction or permanent discontinuation) if deemed at least possibly related to MT-3724 by the investigator
Any Grade $\geq$ 3 electrolyte abnormality that does not resolve, with or without intervention, to Grade $<$ 2 within 72 hours			
Any other Grade $\geq$ 3 nonhematological toxicity excluding the following:	
 
• Nausea, vomiting, or diarrhea, if manageable with antiemetic or antidiarrheal agents within 7 days of onset
 
• Fatigue lasting <math>\leq</math> 72 hours
 
• Grade 3 laboratory abnormalities, if asymptomatic and without a clear clinical correlate
 
		
Hepatotoxicity			
AST and / or ALT OR Bilirubin	$\leq$ 5.0 x ULN (isolated) $\leq$ 1.5 x ULN (isolated)		
 
• No change in treatment
 
• Monitor subject
 

AST and / or ALT OR Bilirubin	$>$ 5 x ULN – 8.0 x ULN (for subjects enrolled with AST/ALT $<$ 3 x ULN) $>$ 1.5 x ULN – 5.0 x ULN		
 
• Temporarily or permanently (see next row) discontinue treatment
 
• Monitor subject
 
• Continue at dose reduced by 1 dose level after abnormal values resolve to Grade <math>\leq</math> 1 or baseline values
 

AST or ALT	$>$ 8.0 x ULN for any period of time (for any subject)		
 
• Permanently discontinue treatment
 

**Table 6-4. MT-3724 Dose Modification Guidance and Specific Management of Toxicities**

		Specific Management	MT-3724 Dose Modification a
	> 5 x ULN for more than 2 weeks (for subjects enrolled with AST/ALT 3-5 x ULN)		
AST and / or ALT  AND  Bilirubin	> 3.0 x ULN (without findings of cholestasis defined as serum ALP < 2 × ULN)  > 2.0 x ULN or INR > 1.5		
 
• Permanently discontinue treatment
 

AST and / or ALT  OR  Bilirubin	> 3.0 x ULN with the appearance of fatigue, nausea, vomiting, right upper quadrant pain or tenderness, fever, rash, and/or eosinophilia (> 5%)  > 5.0 x ULN		
 
• Permanently discontinue treatment
 

NOTE: These are recommendations in situations where a possible relatedness to study drug is assumed. These recommendations cannot consider all clinical circumstances; therefore, the investigator is encouraged to contact the sponsor and/or medical monitors to discuss alternative courses of action.

The number of MT-3724 dose reductions per subject is not limited, except reductions beyond what is outlined in [Table 6-3](#) require consultation with the medical monitor.

ALP = alkaline phosphatase; ALT = alanine aminotransferase; ANC = absolute neutrophil count; AST = aspartate aminotransferase; BP = blood pressure; CLS = capillary leak syndrome; CRS = cytokine release syndrome; INR = international normalized ratio; IRR = infusion-related reaction; ULN = upper limit of normal; TEAE = treatment-emergent adverse event.

a MT-3724 dose reduction by 1 dose level translates to an approximate reduction by 25% to 33%, see [Table 6-3](#). The actual amounts for either agent will be determined by the investigator after consultation with sponsor and medical monitor.

b Clinically significant bleeding is that which requires platelet transfusion.

c Febrile neutropenia is defined as ANC < 1000/µl and fever (a single body temperature reading of > 38.3°C [> 101°F] or a sustained body temperature of ≥ 38.0°C [≥ 100.4°F] for more than 1 hour).

## 6.3 Measures to Minimize Bias: Randomization and Blinding

### 6.3.1 Randomization

The study will be conducted as a single-arm, open-label, non-randomized study, where all eligible subjects will be assigned to MT-3724 treatment.

Assignment of the screening slots and treatment slots will be done on the basis of competitive enrollment across multiple sites.

### 6.3.2 Blinding

Not applicable; this is an open-label study.

## 6.4 Study Treatment Compliance

Because MT-3724 is administered IV, treatment compliance will be monitored through the electronic case report form (eCRF) and source documents (clinic notes and pharmacy records) and clinical observations during study drug infusion. Actual dosing schedule vs planned dosing schedule will be used to assess compliance. Details will be provided in the standalone Pharmacy Manual.

## 6.5 Concomitant Therapy

New medication (either prescription or OTC) or concomitant medication reported by the subject or subject's medical records between the screening medical history and the start of treatment should be reported as concomitant medication. During the treatment and until the STFU visit, concomitant medications will be reported by verbal probes at every visit to the clinic or at every phone contact; in addition, subject's spontaneous reports will be captured.

Except where expressly prohibited (see [Section 6.1.3](#)), the use of concomitant medications is permitted at the investigator's discretion for management of toxicities.

Concomitant use of platelet transfusion for thrombocytopenia, packed red blood cells (RBC) or blood transfusion for anemia or G-CSF for leukopenia are permitted for supportive care at the investigator's discretion, but only after the investigator has properly assessed if the MT-3724 treatment should be modified due to drug-related cytopenia.

Palliative therapy, such as radiotherapy, which spares at least 50% of bone marrow producing regions, to non-target lesions or intrathecal chemotherapy, is allowed at the investigator's discretion after consultation with the medical monitor and sponsor.

While the use of certain immunomodulators is prohibited as described in [Section 6.1.3](#), the use of NSAIDS is permitted.

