### 6.1.3 Excluded Treatments, Medical Devices, and/or Procedures During Study Period

The following treatments are prohibited during the study:

- All systemic treatment for lymphoma
- Radiation therapy to tumor lesions that would serve as target lesions (measurable disease). Palliative radiation therapy to non-target lesions may be permitted (see [Section 6.5](#)).
- Systemic immune modulators, unless used for a treatment-emergent adverse event (TEAE) or as a premedication for MT-3724.
  - The immune modulators include, but are not limited to, systemic corticosteroids at doses > 20 mg/day or prednisone equivalent for more than 1 week, cyclosporin and tacrolimus.
- Any live vaccines from 4 weeks before the start of treatment, during the treatment and after the last dose of MT-3724 while peripheral B cells are depleted.

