### **8.3.1 Radiological Assessment of Tumor Response**

At baseline, both a positron emission tomography-computed tomography (PET-CT) and a computed tomography of diagnostic quality (CT-dq; or MRI) should be collected. Note, if the CT-portion of the PET-CT is of diagnostic quality, a separate CT-dq scan need not be obtained. For follow-up scans, while the same methodology (eg, PET-CT, CT-dq) should be used throughout the study (both PET-CT/CT-dq whenever possible), PET-CT should be used in subjects with fluorodeoxyglucose (FDG)-avid tumor histology while CT-dq and/or MRI should be used in subjects with tumor histology of low or variable FDG avidity. Irrespectively, CT-dq and/or MRI should be used at baseline and in subsequent follow-up scans in lieu of PET-CT if the latter cannot be used at the frequency prescribed per protocol because of access limitations. Methodology may vary per imaging availability, upon consultation with the sponsor. The same technique (eg, slice thickness, field of view) should be used for all scans during the study treatment period.

The radiological tumor response assessment should be performed as indicated in the SoA ([Section 1.3](#)). The original schedule needs to be maintained even if there is a delay in dosing.

Unscheduled tumor response assessment by fluorodeoxyglucose-positron emission tomography-CT (or CT-dq and/or MRI) may be obtained at the investigator's discretion. Complete remission and PR should be confirmed by repeated radiologic evaluation between 4 weeks to 8 weeks after the initial response assessment. For subjects treated beyond progression, radiological evaluation must be repeated in 4 to 6 weeks from initial scan showing progression.

The investigators at each investigational site will determine the preliminary tumor response based on the radiologist's measurement of all anatomic regions involved with the measurable disease according to Lugano Classification for Lymphoma ([[Cheson, 2014](#)], [Section 10.6](#)).

Preferably, all scans from 1 subject should be interpreted by the same investigator and the same radiologist at each investigational site.

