### **8.3.2 Independent Centralized Review of Efficacy Results**

Digital images from all tumor response assessments must be available to be sent to the independent central review (ICR) service at any time during the study. All images sent to the ICR service must be anonymized by the investigational sites and provided digitally as Digital Imaging and Communications in Medicine (DICOM) format. The investigator must assure that the images are of acceptable diagnostic quality and fulfill the requirements outlined in the Imaging Manual. Additional specific information on the handling (ie, collection, shipment, tracking) of the images sent to the ICR will be provided in the Imaging Manual.

The definitive treatment response assessment will be determined by the ICR service at the central imaging laboratory using the Lugano Classification ([Cheson, 2014](#)).

The reviewers at the central imaging laboratory will be board-certified radiologists, experienced and independent radiologists with strong expertise in clinical radiology as well as the use of Lugano Classification in clinical trials with novel hematology-oncology agents. The central reviewers must not be otherwise involved in this study, ie, listed or identified as investigator or sub-investigator who is directly involved in the treatment or evaluation of study subjects. Central reviewers will be isolated from knowledge of investigator PD assessments through read lock procedures and communication controls. Except for the baseline visit, the ICR will be blinded to the subject's identity and all other data (eg, demography, MT-3724 dose modification, TEAEs, disease characteristics).

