### **9.3.2.1        Primary Efficacy Variable (for Part 4)**

The primary efficacy variable is the ORR. The ORR is defined as the percent of subjects with CR or PR determined by the blinded, ICR according to the Lugano Classification for Lymphoma ([Cheson, 2014](#)), relative to the FAS population.

Overall response rate will be summarized by number and percentage of subjects meeting the definition of ORR along with the corresponding 2-sided 95% binomial exact confidence intervals (CI), separately for Parts 3 and 4.

In Part 4, with  $n = 88$  subjects, if  $\geq 23$  ORRs are seen, the null hypothesis is rejected in favor of the alternative hypothesis and the effectiveness of MT-3724 as monotherapy will have been proven.

Subjects with missing disease assessments such that objective response cannot be determined will be assumed to be non-responders in the analysis.

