**Table 10-5. Lugano Classification of Response Assessment in Lymphoma**

Response and Site	PET-CT-Based Response	CT and/or MRI-Based Response
Complete	Complete metabolic response (CMR)	Complete radiologic response (all of the following)
Lymph nodes and extralymphatic sites	5PS score of 1, 2, or 3 a with or without residual mass (see Table 10-6)  It is recognized that in Waldeyer's ring or extranodal sites with high physiologic uptake or with activation within spleen or marrow (eg, with chemotherapy or myeloid colony-stimulating factors), uptake may be greater than normal mediastinum and/or liver. In this circumstance, CMR may be inferred if uptake at sites of initial involvement is no greater than surrounding normal tissue even if the tissue has high physiologic uptake	Target nodes/nodal masses must regress to ≤ 1.5 cm in LD i  No extralymphatic sites of disease
Nonmeasured lesion	Not applicable	Absent
Organ enlargement	Not applicable	Regress to normal
New lesion(s)	None	None
Bone Marrow	No evidence of FDG-avid disease in marrow	Normal by morphology; if indeterminate, IHC negative
Partial	Partial metabolic response	Partial remission (all of the following)
Lymph nodes and extralymphatic sites	Score 4 or 5 on the 5PS (see Table 10-6) with reduced uptake compared with baseline and residual mass(es) of any size.  At interim, these findings suggest responding disease.  At end of treatment (EoT), these findings indicate residual disease	≥ 50% decrease in SPD of up to 6 target measurable nodes and extranodal sites.  When a lesion is too small to measure on CT, assign 5 mm x 5 mm as the default value;  when no longer visible, 0 x 0 mm.  For a node > 5 mm x 5 mm, but smaller than normal, use actual measurement for calculation.
Nonmeasured lesion	Not applicable	Absent/normal, regressed, but no increase
Organ enlargement	Not applicable	Spleen must have regressed by > 50% in length beyond normal.
New lesion(s)	None	None

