### Lugano 5PS Range ([Cheson, 2014](#))

The 5PS ranges from a score of 1 (where no uptake is discernible in the lesion) to a score of 5 (where the uptake in the lesion is markedly increased compared to the uptake in the liver parenchyma). A single 5PS score, which represents the most FDG-avid (ie, metabolically intense) area of disease (across all index and non-index lesions), is assigned for each PET/CT scan in the study, see [Table 10-6](#).

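### Permitted on-study radiotherapy to a non-target lesion can be read as a PET partial response by a central review that is not told of it, and Section 9.3.2 has no rule for such responses

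*Protocol*

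**What the plan says.** **Permission.** Protocol Section 6.1.3 prohibits radiotherapy to target lesions but adds: "Palliative radiation therapy to non-target lesions may be permitted". Section 6.5 sets the terms: palliative therapy such as radiotherapy, sparing at least half of the marrow-producing regions, "to non-target lesions or intrathecal chemotherapy, is allowed at the investigator's discretion after consultation with the medical monitor and sponsor". Exclusion criteria 3a and 12 carry the same exemption.

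**Measurement.** Section 8.3.1 says that "PET-CT should be used in subjects with fluorodeoxyglucose (FDG)-avid tumor histology", with CT or MRI in its place where PET access is limited. Appendix 6 (Section 10.6) assigns one 5-point score (5PS) per PET/CT scan, "which represents the most FDG-avid (ie, metabolically intense) area of disease (across all index and non-index lesions"). In Table 10-5, PET CR is a score of 1 to 3. PET PR is a score of 4 or 5 "with reduced uptake compared with baseline and residual mass(es) of any size". CT-based PR needs at least a 50% fall in the SPD (sum of the products of diameters) of up to six target lesions. Clear progression of a non-measured lesion is a CT criterion for PD.

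**Adjudication.** The ICR decides the Part 4 primary ORR. Section 8.3.2 states that, except at baseline, "the ICR will be blinded to the subject's identity and all other data". Radiotherapy is not excepted.

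**Analysis.** Section 9.3.2.1 has one non-responder rule: "Subjects with missing disease assessments such that objective response cannot be determined will be assumed to be non-responders in the analysis". Section 9.3.2.2 covers censoring and treatment beyond progression. Neither section mentions on-study radiotherapy. The supplied SAP is based on protocol v7.0 (Parts 1 and 2) and the 2007 response criteria, and does not describe the Part 4 analysis.

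**The concern.** Sparing target lesions protects the CT measure, because SPD is taken from those lesions. It does not protect the PET measure, because the 5PS also ranges over lesions that may be irradiated. If the irradiated lesion was the hottest at baseline, the scan's score or maximum uptake can fall although the rest of the disease has not responded to MT-3724. The ICR has no radiotherapy information with which to set that lesion aside.

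Part 4 has no control arm in which such an effect could cancel, and its conclusion rests on a count of at least 23 responders of 88. A radiation effect read as a PR adds to that count, and masked progression lengthens DOR and PFS. Both errors favour the drug.

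**Working it through.** **1. Is each link in the text?**
- Non-target lesions may be irradiated on study: Sections 6.1.3 and 6.5.
- Non-target lesions enter the PET score: Section 10.6.
- PET PR carries no size requirement: Table 10-5.
- The ICR is not told of radiotherapy after baseline: Section 8.3.2.
- No endpoint rule covers it: Sections 9.3.2.1 and 9.3.2.2.

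**2. Which response categories are exposed?**
- PET PR: yes, when the irradiated lesion was the hottest at baseline. If a hotter unirradiated lesion remains, that lesion still sets the score.
- PET CR: only if the unirradiated disease also scores 3 or below. Every subject has at least one measurable lesion (inclusion criterion 5), and target lesions may not be irradiated.
- CT PR: largely protected by the 50% SPD rule. Radiotherapy can only remove an obstacle, such as growth of a non-measured lesion.
- PD: progression of an irradiated non-measured lesion can be masked.

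**3. Reproduce the design.** Inputs from Sections 4.1.2 and 9.1: n = 88, reject at 23 or more responders, null 17%, alternative 32%, one-sided alpha 0.025, stated power 90.4%. With X binomial:
- P(X ≥ 23 | 88, 0.17) = 0.0201
- P(X ≥ 23 | 88, 0.32) = 0.9039

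The stated power reproduces. A cut-off of 22 would give alpha 0.0364, so 23 is the smallest count that meets 0.025.

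**4. Exactly k non-responders scored as responders, true rate 17%.** The false-positive probability is P(Y ≥ 23 − k), with Y binomial on 88 − k subjects at 0.17.

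| k | Probability |
|---|---|
| 0 | 0.0201 |
| 1 | 0.0323 |
| 2 | 0.0504 |
| 3 | 0.0765 (0.076 before the last rounding) |

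**5. As a rate.** Let f be the share irradiated and q the share of irradiated non-responders scored as responders. The observed rate is 0.17 + 0.83 × f × q. The documents give neither f nor q, so these are assumptions.

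| f | q | Observed rate | P(at least 23 of 88) |
|---|---|---|---|
| 2% | 10% | 0.1717 | 0.022 |
| 2% | 25% | 0.1741 | 0.026 |
| 2% | 50% | 0.1783 | 0.033 |
| 5% | 25% | 0.1804 | 0.038 |
| 5% | 50% | 0.1908 | 0.065 |

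**6. Cost of counting every response after radiotherapy as non-response.** If irradiation is independent of response, the rate becomes p × (1 − f).

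| f | Rate at p = 0.32 | Power | Alpha at p = 0.17 |
|---|---|---|---|
| 2% | 0.3136 | 88.0% | 0.016 |
| 5% | 0.3040 | 83.8% | 0.011 |
| 10% | 0.2880 | 74.5% | 0.006 |

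**The case against.** The strongest reply is that the route is narrow and its frequency unknown. It needs PET-based reading, an irradiated lesion that was the hottest at baseline or would have progressed, and other disease that did not respond. Section 8.3.1 asks for both PET-CT and diagnostic CT whenever possible, and Section 9.3.2.2 lists and plots each subject's SPD change, so a PET response without target shrinkage would be visible. Radiotherapy needs consultation with the medical monitor and sponsor, and Section 8.4.2 records it in the eCRF, so affected subjects can be identified. The Imaging Manual and a Parts 3/4 SAP, to which the protocol defers detail, were not supplied and could hold a rule. DOR and PFS are descriptive and do not enter the 23-of-88 decision.

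All of that stands as a limit on size. It does not close the gap. Consultation is a clinical control, not an endpoint rule. A visible discrepancy has no stated consequence for the primary count. Nothing in the protocol says that the Imaging Manual deals with irradiated lesions.

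Three stronger readings are not supported:
- A reader might infer that radiation to a non-target lesion can by itself produce a CR. The hottest remaining lesion still sets the score.
- A reader might infer that the trial's type I error does exceed 0.025. Without a radiotherapy rate that cannot be said; one assumed scenario leaves it at 0.022. Any single misread, whatever its cause, would also cross 0.025, so the one-subject figure shows how thin the margin is, not how often this happens.
- A reader might equate one extra percentage point of ORR with one subject. Rates of 18%, 19% and 20% give 0.037, 0.062 and 0.098, but exactly one, two or three misclassified subjects give the smaller figures in the working.

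**Conclusion.** The point holds within limits. As written, the protocol lets a radiation effect on a non-target lesion be scored as a PET PR in the primary ORR, and lets progression of an irradiated non-measured lesion be masked. CR is exposed only if the unirradiated disease also scores 3 or below, and CT-based PR is largely protected.

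The actual effect cannot be estimated from the documents. The decision rule has little room for it: alpha of 0.020 passes the stated 0.025 with one misclassified non-responder, but stays below it if radiotherapy is rare and seldom changes the reading. These figures assume a true rate of 17%, n = 88 and independent subjects. The conclusion that no rule exists covers the protocol and the supplied SAP only. This should be settled before Part 4 data are read, because a later choice about a few subjects could decide the result.

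**What to change.** - **Section 8.3.2 and the Imaging Manual:** give the ICR the site and date of on-study radiotherapy, and nothing else from the clinical data. Have it exclude irradiated lesions from the 5PS and from evidence of response.
- **Section 9.3.2.1:** add a prespecified sensitivity analysis of the primary ORR in which a CR or PR first documented after on-study radiotherapy counts as non-response.
- **Section 9.3.2.2:** add DOR and PFS sensitivity analyses with that radiotherapy counted as an event.
- **Parts 3/4 SAP:** carry the same wording.

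Voiding every later CR or PR in the primary analysis as well would be redundant once the ICR excludes irradiated lesions. It would discard valid responses in untouched disease and cost power, so it belongs in the sensitivity analysis.

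The cost is wording, plus a transfer of data already in the eCRF. The downsides are a small, limited relaxation of ICR blinding and a conservative sensitivity result (power 88.0% or 83.8% if 2% or 5% are irradiated independently of response). The permission for palliative radiotherapy is unchanged.
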